6.6.1 Primary endpoint

The Niemann-Pick disease type C Clinical Severity Scale (NPC-CSS) measures disease progression⁴ via clinical signs and symptoms in 9 major (ambulation, cognition, eye movement, fine motor, hearing, memory, seizures, speech, swallowing) and 8 minor/modifier (auditory brainstem response, behavior, gelastic cataplexy, hyperreflexia, incontinence, narcolepsy, psychiatric, respiratory problems) domains. A higher NPC-CSS score indicates a clinical worsening, while a lower NPC-CSS score indicates a clinical improvement. A 0-point change in the NPC-CSS score represents a stabilization of disease progression, which is also considered a significant clinical improvement. In the current study, a 15-domain version of the NPC-CSS has been used which omits the ‘hearing’ major domain, and the ‘auditory brain stem’ minor domain from the full 17-domain scale. A modified (5 domain) NPC-CSS score is limited to the assessment of the following 5 major domains: ambulation, cognition, fine motor, speech, and swallowing.

The primary endpoint in this Extension Phase is success measured on the 5-domain NPC-CSS score from the Extension Phase baseline (Visit 7) to the end of treatment in the Extension Phase (Visit 9). Success is defined as no change or a decrease in the 5-domain NPC-CSS score from Visit 7 to Visit 9.

The primary endpoint will be summarized using a frequency table. The primary statistical analysis of comparing the proportion success with the null proportion of 0.10 will be done using a one-sided Fisher’s Exact Test, expecting an increase in the success rate. The statistical result (one-sided p-value and exact 90% confidence interval⁵) will be added to the frequency table. This analysis is considered to be exploratory.

The modified (5 domain) NPC-CSS score will also be presented descriptively including change from baseline values (Visit 9 versus Visit 7). This modified score will range between 0 and 25. If collected, data at Visit 1 of the parent study will also be included.

In addition, a spaghetti plot presenting the total modified (5-domain) NPC-CSS scores of each patient through time will be created.

⁴ Cortina-Borja et al. Annual severity increment score as a tool for stratifying patients with Niemann-Pick disease type C and for recruitment to clinical trials. *Orphanet Journal of Rare Diseases* (2018) 13:143.

6.6.2 Secondary endpoints

As PK is handled by an external company, there are no analyses for secondary endpoints to add here.

6.6.3 Exploratory endpoints

All exploratory endpoints for the Extension Phase will be presented using the mITTe population, and all individual data will be listed as well. For all exploratory efficacy endpoints, the change from Visit 7 to Visit 9 will be evaluated. Except for 15-domain NPC-CSS and modified (5-domain) NPC-CSS, no statistical analysis other than descriptive statistics will be done. No plots will be created.

Measurement of Ataxia and Functioning

- SARA total score
- SCAFI total score
 - 9HPT-D
 - 9HPT-ND
 - 8MWT
 - PATA test

Descriptive statistics will be used to summarize the endpoints above at each visit.

The subscores of the SARA score (gait, stance, sitting, speech disturbance, finger chase, nose-finger test, fast alternating hand movements, heel-shin slide) will not be summarized separately, and only listed.

The average SCAFI subscores (8MW_avg, 9HPT-D_avg, 9HPT-ND_avg and PATA_avg) as determined according to Section 10.1, following the scoring manual, will also be summarized with descriptive statistics.

The changes in SARA total score, SCAFI total score, and the SCAFI subscores (8MW_avg, 9HPT-D_avg, 9HPT-ND_avg and PATA_avg) between Visit 7 and Visit 9 will be descriptively summarized in tabular format as well.

Measurement of Health-related Quality of Life

The results of EQ-5D-5L as well as the EQ-5D-Y will be combined into a 5-digit number presenting the health status of the subject. Frequency tables will be presented per visit for the 5 domains, as well as for the 5-digit number of the EQ-5D-5L and the EQ-5D-Y separately.

Note that if a patient turns 18 before Visit 7, this patient can have results on EQ-5D-Y in the Parent Study, and results on EQ-5D-5L in the Extension phase Visit 7 to 10. For this reason, separate QoL presentations will be created for Extension phase I, using Visit 7 measurements as baselines. The EQ-VAS score will be summarized by visit using descriptive statistics in a combined manner for patients aged < and ≥ 18 years (using Visit 7 age values).

Measurement of Global Impression

The three CGI-S scores (scored by treating physician, caregiver, and patient) will be summarized using descriptive statistics and frequency tables for each visit.

Descriptive statistics and frequency tables will also be used to summarize the three CGI-C scores (treating physician, caregiver, and patient) between Visit 7 and Visit 9.

Note that CGI-C is mentioned as CGI-I in the eCRF.

It is important to realize that the CGI-S and CGI-C scores per visit for each patient as provided by the caregiver may be based on varying caregivers and hence additional variation is introduced. No correction for this variation can be done and a footnote will be added to the table to describe this situation.

Measurement of Disease Progression

Descriptive statistics will be provided for (15 domain) NPC-CSS total sum score, including Visit 1 of the parent study if collected. Change from baseline (Visit 9 versus Visit 7) will be presented descriptively as well. The sum of the major domains (ranging from 0-40), the sum of the modifier domains (ranging from 0-14), and each domain subscore at each visit will not be presented descriptively, and only included in listings.

The ASIS score is obtained by dividing the total NPC-CSS severity score of a patient by the age of the patient (at Visit 9), providing a measure of the rate of disease progression in individual patients. Descriptive statistics for ASIS will be provided, including the change in ASIS score from Visit 7 to Visit 9.

6.6.4 Additional exploratory endpoints

For all additional exploratory endpoints as described in Section 4.2.4, descriptive presentations will be made and the change from Visit 7 to Visit 10, Visit 9 to Visit 10, Visit 10 to Visit 12, and Visit 1 to Visit 12 will be evaluated descriptively. No plots will be created, and no statistical analysis done.

These presentations include the endpoints as mentioned above in sections 6.6.1, 6.6.2, and 6.6.3 that will be presented as exploratory using only descriptive statistics for the Extension phase on data collected after Visit 10. For EQ-5D-5L as well as the EQ-5D-Y, a different questionnaire could be used between Visits 10 and 12 if a patient turns 18 before Visit 10, and for this reason separate QoL presentations will be created for Extension phase II, using Visit 10 measurements as baselines. The EQ-VAS score will be summarized by visit using descriptive statistics in a combined manner for patients aged < and ≥ 18 years (using Visit 10 age values).

For presentations on efficacy data collected after Visit 10, no imputations or LOCF is considered necessary.

6.6.5 Other additional statistical analyses

No other additional statistical analyses are foreseen.

6.7 Safety and tolerability evaluation

The safety and tolerability evaluation for the extension study is similar to what is described for the Parent study (see Section 5.7), with the remark that the evaluation is limited to the Extension phase only and Visit 7 is considered the baseline. For the AE presentation per treatment cycle, the cycles for Extension phase are as follows:

- Treatment cycle Extension phase I: the period between start of first treatment at Visit 7 and 24 hours after last dose at Visit 9.
- Washout cycle Extension phase I: starts 24 hours after last dose at Visit 9 until and includes Visit 10.
- Treatment cycle Extension phase II: the period between start of first treatment at Visit 10 and 24 hours after last dose at Visit 12.
- No washout cycle is defined for Extension phase II.

Note that for those patients that do not transition seamlessly to the Extension phase, additional prior medication/adverse events may be collected at the start of the Extension phase, and these will be presented separately from the prior medication/adverse events of the Parent phase.

Physical examination, which is collected twice during the Extension phase, will be presented as follows: general physical examination data will be tabulated and listed per visit. The summary table will include number/percentage of patients with normal or abnormal observations and NCS/CS frequencies/percentages for abnormal observations per visit.

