6.2.5 Electrocardiograms (ECGs)

During the study, 12-lead ECGs will be performed approximately at the time points designated on the schedule of events (Appendix 3A for "naïve" patients and Appendix 3B for "non-naïve" patients). In addition, ECGs may be performed at other visits at the discretion of the Investigator if the findings from a previous ECG was clinically relevant.

The patient must be in a supine position in a rested and calm state for at least 5 minutes before ECG assessment is conducted. If the patient is unable to be in the supine position, the patient should be in the most recumbent position possible.

All ECGs should be performed in a standardized method prior to blood draws or other invasive procedures.

Each ECG must include the following measurements:

Corrected QT, and whether the ECG is Normal, Abnormal NCS (not clinically significant), or Abnormal CS (clinically significant) for the patient.

The Principal Investigator or designated site physician will review and sign all ECGs. Results must be summarized in writing and classified as normal; Abnormal NCS (not clinically significant), or Abnormal CS (clinically significant) for the patient. Intervals of the ECG will be recorded in the eCRF. Once signed, the original ECG tracing will be retained with the patient's source documents. At the request of the Sponsor, a copy of the original ECG will be made available.

Due to COVID-19, ECGs may not be able to be collected at the designated timepoints in the schedule of events (e.g. if visits are skipped and replaced by remote visits or postponed) or if qualified study team members/ appropriate equipment are not available/accessible. The Sponsor's Medical Expert, Medical Monitor, and DSMB deem the risk posed by ECGs not being collected at the designated timepoints is acceptable in the context of remote visits where study staff will enquire regarding the health and wellbeing of the patient and assess for adverse events. This decision was based on the nature of the drug, the available non-clinical and clinical data for N-Acetyl-L-Leucine and N-Acetyl-DL-Leucine (see Section 1), and the safety profile (no reports of cardiac issues, including QTc prolongation) observed in this ongoing, open-label study (and also in other ongoing trials with IB1001) to date. ECGs will be routinely collected at Visit 9 in the Extension Phase, allowing for further assessment of any cardiac effects.

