6.4.5 Electrocardiograms (ECGs)

During the Extension Phase, one 12-lead ECG will be performed at the time point designated on the Extension Phase schedule of events (Table 6.1), following the procedures and policies provided in Section 6.2.5 of the Parent Study.

In addition, ECGs may be performed at other visits at the discretion of the Investigator.

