5.7.3 Vital Signs

Vital sign data consist of measurements for pulse rate and systolic/diastolic blood pressure (sitting). Vital signs will be summarized and listed per visit (protocol visits). Change from baseline will be calculated and presented as well, using the same summary statistics. Visit 2 is considered the baseline visit for vital signs; in case Visit 2 is missing, the Visit 1 measurement will be used as baseline instead. If applicable, vital sign measurements collected as additional/unscheduled assessments (i.e. apart from those per protocol) will only be listed and will not be used in summary statistics. The SAF population is used for the presentations.

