5.7.4 Electrocardiography (ECG)

ECG outcome results (corrected QT interval and normal/abnormal result) will be presented descriptively per protocol visit. If applicable, ECG measurements collected as additional/unscheduled assessments (i.e. apart from those per protocol) will only be listed and will not be used in summary statistics. The SAF population is used for the presentations.

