For the full Extension Phase, the measurement at Visit 7 is considered the baseline. In case of missing Visit 7A data for safety measurements (e.g. for safety lab), and Visit 7B has occurred within 1 (+6) days of Visit 6, the Visit 6 data from the Parent Study should be used instead (data are not being re-entered in the database): see also Section [2.2.2](#) for clarification. No screen failures will be present in the data.

No screen failures will be present in the data.

For the full Extension Phase, a treatment emergent adverse event (TEAE) is defined as an adverse event (AE) that appears during or after the start of study treatment in the Extension Phase at Visit 7B and was absent before. As a consequence, AEs occurring during the washout phase between Visit 9 and Visit 10 will also be considered treatment emergent.

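### The planned ECG summaries contain no within-patient QTc comparison, and the one scheduled Extension ECG (Visit 9A) has no tabulated comparator

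*SAP*

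**What the plan says.** **Parent Study.** SAP 5.7.4 states that "ECG outcome results (corrected QT interval and normal/abnormal result) will be presented descriptively per protocol visit". It names no change from baseline and no shift, and unscheduled ECGs are only listed. For vital signs, SAP 5.7.3 adds that "Change from baseline will be calculated and presented as well, using the same summary statistics". SAP 5.7.2 makes the same provision for quantitative laboratory data.

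**Extension Phase.** SAP 6.7 handles safety much as in the Parent Study, except that "the evaluation is limited to the Extension phase only and Visit 7 is considered the baseline". SAP 6.1 sets the general rule: "For the full Extension Phase, the measurement at Visit 7 is considered the baseline". If Visit 7A safety data are missing and Visit 7B falls within the permitted window after Visit 6, "the Visit 6 data from the Parent Study should be used instead".

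**ECG collection in the Extension.** Protocol Appendix 6, section 6.4.5: "During the Extension Phase, one 12-lead ECG will be performed at the time point designated on the Extension Phase schedule of events". Table 6.1 and SAP 2.5.2 place that ECG at Visit 9A, with another at early termination.

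**Purpose given to it.** Protocol 6.2.5, after discussing ECGs missed because of COVID-19, adds: "ECGs will be routinely collected at Visit 9 in the Extension Phase, allowing for further assessment of any cardiac effects".

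**The concern.** QTc varies between patients, so the informative summary in a small single-arm study is the change within a patient. The plan provides this for vital signs and laboratory values but not for QTc.

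By-visit summaries are a weak substitute because the contributing patients can differ from visit to visit. The in-person Visits 3 and 5 may be skipped when COVID-19 makes them infeasible, and the sponsor expects only 60% to 70% of patients to enter the Extension. A mean QTc at Visit 9A that differs from the mean at Visit 1 could reflect who remained as much as what the drug did. A patient whose QTc rises, or whose ECG moves from normal to abnormal, would not be identified as such in any planned summary.

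This bears on a stated aim, since long-term safety and tolerability is a secondary objective of the Extension Phase.

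**Working it through.** The plan gives no figure to reproduce. The check sets the ECG schedule beside the planned analyses.

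**Step 1: where ECGs are scheduled** (Protocol Appendix 3A and 3B, Protocol Table 6.1, SAP 2.5.1 and 2.5.2).

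| Visit | Drug status | ECG scheduled |
|---|---|---|
| 1 | before drug | yes |
| 2 | before first dose | no |
| 3 | on drug | yes |
| 4 | end of treatment | no |
| 5 | washout | yes |
| 6 | end of washout | no |
| 7A, 7B | Extension baseline | no |
| 8 | on drug | no |
| 9A | on drug (last Period I dose is at 9B) | yes |
| 9B, 10, 11, 12 | various | no |

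Leaving early termination aside, there are 3 scheduled ECGs in the Parent Study and 1 in the Extension.

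**Step 2: apply the SAP's Extension baseline rule.** Scheduled ECGs at Visit 7: 0. Scheduled ECGs at the fallback, Visit 6: 0. Visit 7 to Visit 9A pairs per patient: min(0, 1) = 0. Discretionary ECGs cannot fill the gap in the tables, because unscheduled ones are excluded from summaries.

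**Step 3: count the planned change analyses.**

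| Safety measure | Change from baseline specified |
|---|---|
| Laboratory (SAP 5.7.2) | yes |
| Vital signs (SAP 5.7.3) | yes |
| ECG (SAP 5.7.4) | no |

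The table lists (14.3.6 and 14.3.9) say only ECG. That does not decide the matter, because the vital-sign entries are equally brief; the omission is in the text of 5.7.4.

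**Step 4: on-treatment coverage in the Parent Study.** Visit 3 carries the only scheduled on-drug ECG. Visit 4 cannot be skipped but has no ECG. ECG is not named in the list of remote assessments (Protocol 3.1.2.5.3). The early-termination visit is preferably 7 to 14 days after the last dose, so its ECG would usually be off drug. A patient who skips the in-person Visit 3 therefore has no scheduled on-drug ECG in the Parent Study.

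**Step 5: what a Visit 1 reference would give.** The Visit 1 ECG is scheduled for naïve and non-naïve patients alike. Each patient with ECGs at Visit 1 and Visit 9A gives one pair. The nominal gap is about 14 + 84 + 365 = 463 days (Visit 1 at Day -14, Visit 6 at Day 84, Visit 9A at Extension Day 365), assuming a seamless transition.

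For the precision of such a pair, the documents give no SD, so 10 to 25 ms is an assumption. The half-width of a two-sided 90% interval is t(0.95, n-1) × SD / √n:

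| Assumed SD of QTc change (ms) | n = 20 (planned Extension) | n = 36 (planned mITT) |
|---|---|---|
| 10 | 3.9 | 2.8 |
| 15 | 5.8 | 4.2 |
| 20 | 7.7 | 5.6 |
| 25 | 9.7 | 7.0 |

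Both values of n assume that every planned patient has both ECGs. Missing ECGs would widen the intervals.

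**The case against.** **The data are not lost.** A reader might infer that the one-year ECG is uninterpretable or cannot show a drug effect. The documents do not support that. ECGs are listed per patient in both phases (listings 16.2.6.4 and 16.2.6.9) under the same subject numbers, so Visit 1 can be paired with Visit 9A by hand. By-visit QTc and normal/abnormal results are still tabulated, and in the Parent Study they cover before, on and off drug. Every ECG is classed by a physician, and a clinically significant new finding can be recorded as an adverse event. This stands, and it limits the point to the planned summaries.

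**The Visit 7 baseline is not the root cause.** SAP 5.7.4 uses no ECG baseline, so naming Visit 7 removes no QTc change analysis that was otherwise planned. In the Parent Study the general rule in SAP 5.1 already falls back to Visit 1 when Visit 2 has no value; only the change display is missing. This also stands. The Visit 7 rule matters because adding a change table under it would still produce nothing for the Extension.

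**The protocol does not rest its acceptance of missed ECGs on Visit 9.** A reader might infer from Protocol 6.2.5 that the Visit 9 ECG is there to make up for them. The section justifies the risk by the remote visits, the nature of the drug, the existing data and the observed safety profile. The Visit 9 sentence follows as an addition. It does say, however, that this ECG allows further assessment of cardiac effects, and the planned tables serve that poorly.

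**A paired change is still uncontrolled.** There is no comparator arm, and more than a year separates Visit 1 from Visit 9A, in a population that includes growing children. Pairing removes the changing patient mix but not confounding with time. True, and the result should be labelled accordingly.

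**Conclusion.** The point holds as a gap in the planned safety summaries. No within-patient QTc comparison is planned in either phase. Under the Extension baseline rule, none can be computed from scheduled ECGs for any patient, because neither Visit 7 nor Visit 6 has one. The single on-drug ECG after a year of treatment is left with no tabulated pre-drug comparator.

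This rests on the visit schedules and SAP text as written. It assumes that by-visit description in SAP 5.7.4 does not silently include a change, which the explicit wording for laboratory values and vital signs makes the natural reading. The documents do not allow an estimate of how many patients lack an on-treatment ECG, or of how far by-visit means would mislead.

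The change is worth making before the tables are programmed. It concerns completeness of safety reporting; the primary analysis and the efficacy conclusions are unaffected.

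**What to change.** In SAP 5.7.4 and 6.7, name the Parent Visit 1 ECG as the ECG reference for both phases, as a stated exception to the Visit 7 baseline. There is precedent: SAP 6.6.1 and 6.6.3 already bring Parent Visit 1 NPC-CSS values into Extension displays. Then tabulate:

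- paired QTc change from Visit 1 to Visit 3 (on drug), Visit 5 (off drug) and Visit 9A (on drug), in patients with both ECGs, with the number of pairs at each visit;
- the shift from Visit 1 in the three recorded classes: normal, abnormal not clinically significant, abnormal clinically significant;
- the number of patients with no on-treatment ECG, by phase.

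Add a footnote that the change is uncontrolled and that the Visit 9A comparison spans more than a year.

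**Cost:** a few sentences and one extra table on data already collected, with no new ECG. Patients without a Visit 1 ECG drop out of the pairs, so the by-visit summaries should be kept alongside.

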6.8 Scheduled visits, dosing, and treatment compliance

The presentation for the Extension study phase is similar to what is described for the Parent study (see Section 5.8), with the remark that the evaluation is limited to the Extension phase only and Visit 7 is considered the baseline. Compliance calculations are done for Extension phase I and II separately, with Visit 7 or Visit 10 as reference/first dose date.

7 CHANGES TO PROTOCOL AND OTHER RELEVANT REMARKS

The SAP is based on two protocol versions: a US version and a general version. The difference between the two is a difference in inclusion criteria, which will impact the CDISC datasets as well as the documentation (including annotated CRF) thereof.

Instead of Bland-Altman analyses of outcome scores at Visit 1 vs Visit 2, Visit 3 vs Visit 4, and Visit 5 vs Visit 6 as described in the protocol for the Parent study, an ICC method for agreement between the visits will be used instead to assess the stability of the outcome, as described in section 5.6.4. This is because no per-rater information is available in the dataset to be received, only an averaged or agreed value.

Regarding CI-S, the protocol is stating that for each assessment, the videos will be labeled as Video A, B, C, D, E, F. This is however not present in the DTA and test data from [REDACTED] and is therefore removed from the SAP.

For Quality-of-Life measures, since the scoring is done for children with the -Y and for adults with the -5L, tabulations and analyses will be done separately for the corresponding age groups. The proposed statistical analysis on the VAS in the protocol has also been replaced with descriptive statistics.

NPC-CSS has been added to the protocol during the addition of the Extension study, to be collected at Visits 1, 7, 8, 9 and 10. As a consequence, only for a limited number of patients has this value been collected during screening (Visit 1) of the parent study. Considering these measurements are only of importance for the Extension phase, presentation of Visit 1 NPC-CSS will not be done for the Parent study but will be included in the CDISC datasets and analyses for the Extension phase.

For the parent study, sparse PK sampling will be collected for biochemical analysis to characterize the pharmacokinetics of N-Acetyl-L-Leucine in patients with NPC. For the extension study, full PK profiles will be collected at Visit 7 and Visit 9. Creation of descriptive displays and reporting of these data is outside the scope of this statistical analysis plan. PK concentration data and PK parameters will be included in CDISC domains, after receipt. For the Parent phase a listing of PK concentration data will be created for inclusion in the Parent phase interim CSR, since the full PK report will only be available after the end of the Extension phase. Furthermore, urine tests for N-Acetyl-D-Leucine are handled by the same lab but will be included in the clinical database and will therefore be part of the CDISC datasets.

Regarding the sensitivity analysis (imputation of value -1) for missing data in the primary and secondary analyses: this is only applied to the primary analysis.

Regarding the LOCF/assumption of value 0 for missing data: this is only applied to the primary and one key secondary endpoint as stated in this SAP.

The investigation of the intra-rater correlation cannot be performed, since the [REDACTED] data do not differentiate the data per rater but rather provide an average or agreed value. Therefore, this analysis has been removed from the SAP.

Considering the primary endpoint of the Extension phase is a different one than the primary endpoint of the Parent Study, the trial is called successful only when the primary endpoint of the Parent Study is positive. All analyses of the Extension phase on data collected until Visit 10 are considered secondary to ones of the Parent Study. All presentations in the Extension phase on data collected after Visit 10 are exploratory and descriptive.

Baseline characteristics/subgroups are defined slightly different in this SAP as compared to the protocol, but only to provide more clarity on the precise subgroups. The protocol used for the adaptations for the extension phase, also has adjustments for the subgroups for the parent phase (SARA gait subtest and gender). However, the parent phase SAP was based on an earlier version of the protocol and does not include these subgroups. Therefore, these subgroups are not added to the SAP.

The protocol has an ITTe analysis population and an PPSe analysis population defined. Since neither of these analysis populations are not used for any efficacy analysis in the extension phase, they are removed from the SAP. Consequently, there is no need for a BDRM to decide on minor/major protocol deviations for the extension phase.

For some patients, repeat visits were scheduled if measurements could not be fully handled during the agreed visit. Repeat visits will be listed for BDRM, and during BDRM or Clean File meeting it will be decided how the repeat data will be handled for analysis. Decisions will be documented prior to Database lock.

